4.2. SCHEDULE OF EVENTS

Schedule of events can be found in Section 6.1.4 (Table 3) of the protocol.

4.3. Changes to Analysis from Protocol

The protocol uses the term clinically driven and ischemia driven interchangeably. This SAP defines
revascularization events accordingly to the term "clinically driven" as this is consistent with the CEC
adjudication form.

Document: T:\PROJ\Medinol\CXA27472\06 Biostatistics\Documentation\SAP\Final

1.0_08Aug2018\JNIR01_SAP_Final V1.0_08Aug2018.docx

Author: [name] Version Number: Final V1.0 Version Date: 08Aug2018

Template No: CS TP BS016 Revision 4 Reference: CS WI BS005

Effective Date: 01Apr2016

Copyright © 2009, 2010, 2012, 2016 Quintiles Transnational Corp. All rights reserved.

- The protocol defines the as-treated (AS) population which contains only those Japanese patients who
 received the study stent. However, this population is not used in any of the analyses and will not be
 defined in this SAP.
- The protocol suggests a sensitivity analysis based on modified definitions of peri-procedural myocardial infarction (universal definition and modified SCAI definition). This analysis will not be performed for the purpose of assessing the non-inferiority of JNIR01 to BIONICS in terms of Target Lesion Failure at 12 months.

5. PLANNED ANALYSES

The following analyses will be performed for this study:

- Analysis of the primary endpoint and main secondary endpoints after 1 year follow-up
- · Final Analysis after 5 years follow-up

Except for analyses involving the use of data from the BIONICS trial and analyses of quantitative coronary angiography and electrocardiogram from Core Laboratories, all final, planned analyses identified in this SAP will be performed by IQVIA Biostatistics following sponsor authorization of this SAP and database lock.

The primary analysis, non-inferiority of JNIR01 Target Lesion Failure at 12 months (TLF₁₂) to the BIONICS TLF₁₂, and all analyses involving the use of data from the BIONICS trial will be conducted by Cardiovascular Research Foundation (CRF) following the specifications given in this SAP and using data from the JNIR01 and the BIONICS trials.

Analyses of quantitative coronary angiography and electrocardiogram data from Core Laboratories, Cardiovascular Research Foundation, will also be performed by Cardiovascular Research Foundation.

6. ANALYSIS SETS

Agreement and authorization of patients included/excluded from each analysis set will be obtained from Medinol or representative prior to database lock of the trial.

6.1. ALL PATIENTS SCREENED SET [APSS]

The All Patient Screened Set will include all patients who signed an informed consent.

6.2. FULL ANALYSIS SET [FAS]

The Full Analysis Set (FAS) will contain all enrolled Japanese patients regardless of whether they were given MedJ-01.

Document: T:\PROJ\Medinol\CXA27472\06 Biostatistics\Documentation\SAP\Final

1.0_08Aug2018\JNIR01_SAP_Final V1.0_08Aug2018.docx

Author: [name] Version Number: Final V1.0 Version Date: 08Aug2018

Template No: CS TP BS016 Revision 4 Reference: CS WI BS005

Effective Date: 01Apr2016

Copyright © 2009, 2010, 2012, 2016 Quintiles Transnational Corp. All rights reserved.

Patients are considered enrolled after the guidewire has successfully been passed beyond the target lesion. If the study stent could not be implanted due to reasons that are not related to study device, the patient will be de-registered and will not be considered part of the FAS. Patients not receiving the study stent after it has been advanced beyond the guiding catheter will be analyzed in the FAS. Patients enrolled in the trial with major deviations will also be analyzed in the FAS.

6.3. PER PROTOCOL SET [PPS]

The Per Protocol Set (PPS) will contain all patients who receive the study stent with no major protocol violations. Major protocol violations include enrollment of a patient:

- · whose informed consent was not properly obtained
- who did not meet all of the inclusion or exclusion criteria
- who did not receive the study stent due to any reason
- who did not receive at least 12 months of Dual Antiplatelet Therapy (DAPT) post baseline procedure. Details of DAPT to be received post-procedure are given in Section 6.4.9.3 of the protocol.

Major protocol violations leading to exclusion from the PPS will be summarized using the FAS.

6.4. SAFETY ANALYSIS SET [SAF]

The Safety Analysis Set (SAF) will include all patients who signed an informed consent and have had any trial related activities including de-registered patients. Screen failure patients will not be included in the SAF.

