6.1.5 Equipment to Be Used for Assessing the Clinical Variables

The Angiographic Core Lab will perform a qualitative and quantitative coronary analysis (QCA) (Pie Medical CAAS Workstation v. 5.11.2 Software) assessment of all target lesions preprocedure, post-procedure. Morphological characteristics (calcification, tortuosity, bifurcation, presence of thrombus), TIMI flow and blush will be assessed at baseline. Complications (no reflow, slow reflow, abrupt closure, new or worsening thrombus, distal embolization, perforation and dissection by NHLBI criteria) will be assessed intra-procedurally and at the end of the baseline procedure.

6.1.6 **Procedures for the Replacement of Subjects**

Discontinued subjects will not be replaced. De-registered subjects will not count towards the sample size of approximately 100 subjects and will not be included in the FAS but will be included in the safety analysis set and will be followed until resolution of any adverse events related to study procedures.

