6.4.3.1 De-registered Subjects

In case of de-registration, the de-registered subjects will be followed until resolution of any adverse event related to study procedures (refer to instructions for de-registration in the trial's Site Binder).

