7.3 Analysis of Safety

All adverse events collected will be coded using MedDRA, to preferred term and system organ class and summarized for the Safety Analysis Set and de-registered subjects. AEs will be summarized showing the number of events and the number of patients with each event.

A by-patient listing of (serious) adverse events / UADE, including identification of the event by investigator term, date and time started, intensity, relationship to study drug, action taken, and date and time resolved, will be presented in the data listings.

A by-patient listing of deaths will be presented.

Device deficiency is defined as the inadequacy of a medical device with respect to its identity, quality, durability, reliability, safety, or performance. Device deficiencies include malfunctions, use errors, and inadequate labeling.

Device malfunction/deficiencies and any (serious) adverse events associated with device malfunction/deficiencies will be tabulated by treatment arm and overall. All randomized subjects, including de-registered subjects, will be included in the analysis.

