Procedure success is defined as achievement of a final in-stent diameter stenosis of <50% (by QCA) using the assigned device and/or with any adjunctive devices, without the occurrence of cardiac death, Q wave or non-Q wave MI, or repeat revascularization of the target lesion during the hospital stay.

ADVERSE DEVICE/DRUG EFFECTS

See Section 14 for definitions of adverse device/drug effects (serious, anticipated, and unanticipated)

ADVERSE EVENTS

See Section 14 for definitions of adverse events (non-serious and serious)

ANALYSIS DATA SETS

Full Analysis Set (FAS)

Patients are considered enrolled after the guidewire has successfully been passed beyond the target lesion. If the study stent could not be implanted due to reasons that are not related to study device, the patient will be de-registered and will not be considered part of the full analysis set. Patients not receiving the study stent after it has been advanced beyond the guiding catheter will be analyzed in the full analysis set. Patients enrolled in the trial with major deviations will also be analyzed in the full analysis set.

Per Protocol (PP Population)

Patients who receive the study stent with no major protocol deviations as detailed in section 7.1 will be included in the Per Protocol Analysis Set.

Safety Analysis Set

The safety analysis set will include all subjects who signed an informed consent and have had any trial related activities including de-registered subjects.

ANGINA PECTORIS

CCS Classification of Stable Angina

- I. Ordinary physical activity does not cause angina, such as walking or climbing stairs. Angina occurs with strenuous or rapid or prolonged exertion at work or recreation.
- II. Slight limitation of ordinary activity. Angina occurs upon walking or climbing stairs rapidly, walking uphill, walking or stair climbing after meals, or in cold, or in wind, or under emotional stress, or only during the few hours after awakening. Angina occurs if

walking more than two blocks on the level or climbing more than one flight of ordinary stairs at a normal pace and in normal conditions.

- III. Marked limitation of ordinary activity. Angina occurs upon walking one or two blocks on the level or climbing one flight of stairs in normal conditions and at a normal pace.
- IV. Inability to carry on any physical activity without discomfort. Angina syndrome may be present at rest.

		Clinical Circumstances		
		Α	В	С
		Develops in presence of	Develops in the	

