17. SAFETY OUTCOMES

All outputs for safety outcomes will be based on the Safety Analysis Set unless otherwise specified.

Only data of the JNIR trial will be presented for the safety outcomes. In particular, there will be no statistical comparisons between JNIR and BIONICS trials for the safety outcomes.

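### Adverse-event tables default to a Safety Set that includes unstented, briefly followed de-registered patients, which would dilute device-related and late-onset percentages

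*SAP*

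**What the plan says.** **Who is in the set.** SAP 6.4 takes consented patients who "have had any trial related activities including de-registered patients" and leaves out screen failures. Protocol 21.1 has the same definition: "have had any trial related activities including de-registered subjects".

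**Who is de-registered.** SAP 6.2: "If the study stent could not be implanted due to reasons that are not related to study device, the patient will be de-registered". These patients are outside the Full Analysis Set (FAS). Protocol 6.1.6 adds: "De-registered subjects will not count towards the sample size of approximately 100 subjects". No expected number or cap is given.

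**How long they are followed.** Protocol 6.4.3.1: "the de-registered subjects will be followed until resolution of any adverse event related to study procedures". For other subjects, Protocol 14.5.1 collects AEs until 5 years from enrollment.

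**What is tabulated.** SAP 17: "All outputs for safety outcomes will be based on the Safety Analysis Set unless otherwise specified". SAP 17.1 then reports AEs, SAEs, USADEs, severity and relationship to procedure, device or embedded drug as numbers and percentages of patients. The summaries are cumulative, from hospital discharge to 5 years. No denominator based on follow-up is given for them.

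**Exposed patients.** Protocol 7.1 describes an as-treated population of stent recipients. SAP 4.3 drops it: "However, this population is not used in any of the analyses". The Per Protocol Set requires the stent, but also 12 months of DAPT and no other major violation, and SAP 15.1.3 uses it only to repeat the primary analysis.

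**The concern.** The objective in SAP 3 is the safety and efficacy of MedJ-01. An event caused by the implanted stent or its drug can arise only in a patient who carries the stent, and a late event can be recorded only while the patient is followed. A patient de-registered without a procedure-related event meets neither condition, yet could still be counted as event-free at every time point to 5 years.

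If so, the percentages that bear most directly on the device would depend partly on how many unstented patients were de-registered, which says nothing about the stent. For AEs other than the endpoint events, for USADEs and for relatedness, the SAP specifies no other table from which an exposed-patient rate could be read.

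**Working it through.** The documents state no AE rate, no Safety Set size and no number de-registered, so there is no planned figure to reproduce. The check has three steps.

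**1. Is the Safety Set total the denominator?** SAP 17.1 does not say so outright. The relevant passages are:

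- SAP 7.1 takes percentages out of the observations available. That rule removes missing or unknown values, and a patient with no AE record does not have a missing value.
- SAP 8.3 puts all available data into the safety analysis. It says only that some efficacy analyses exclude patients with inadequate follow-up.
- Where the SAP wants a denominator based on follow-up, it writes one: SAP 15 and 15.2.2.1 for binary endpoints, and SAP 17.6.3 for visit compliance.
- SAP Appendix 1 provides table columns for JNIR and Bionics only, with none for de-registered patients.

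The natural reading is therefore the whole set. It remains an inference, because the table templates are a separate document (SAP 9).

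**2. Dilution of device- or drug-related and late-onset events.** Inputs are 100 FAS patients (approximately 100 in Protocol 6.1.1) and d de-registered patients on top of them (assumed). Let r be the proportion of FAS patients with the event, and assume no such event is recorded among the de-registered.

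- Reported proportion = 100r / (100 + d) = r × 100/(100 + d)
- Relative loss = d / (100 + d)

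| d (assumed) | Factor | Relative loss | A 10% rate is shown as |
|---|---|---|---|
| 1 | 0.990 | 1.0% | 9.9% |
| 2 | 0.980 | 2.0% | 9.8% |
| 5 | 0.952 | 4.8% | 9.5% |
| 10 | 0.909 | 9.1% | 9.1% |
| 20 | 0.833 | 16.7% | 8.3% |

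The 10% rate is only an illustration.

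**3. Direction for other events.** Let q be the proportion of de-registered patients with a recorded event. The pooled proportion is (100r + dq)/(100 + d), which is below r only when q is below r. De-registered patients have undergone angiography and wire crossing, and their procedure-related events are followed. For any-AE, any-SAE and procedure-related rates, q may therefore exceed r, and because the tables are cumulative those early events carry forward. As a hypothetical example, take r = 20% and d = 5. With no events among the five, the table shows 20/105 = 19.0%. With two of the five affected, it shows 22/105 = 21.0%.

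**The case against.** Several points on the other side stand.

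- A reader might infer that every safety percentage is affected. The documents do not support that. SAP 17 allows exceptions: screening laboratory values (SAP 17.4) and visit compliance (SAP 17.6.3) use the FAS.
- A reader might also infer that the dilution hides stent thrombosis or repeat revascularization. It does not. Death, MI, TLR/TVR, stent thrombosis and site-reported bleeding are secondary efficacy variables analysed on the FAS (SAP 15.2), with denominators based on follow-up or with Kaplan–Meier censoring. One qualification is that Protocol 14.3.1 classes all MIs, unscheduled revascularizations and stent thromboses as SAEs. The same events therefore also appear in the SAE tables, over the larger set.
- Protocol 7.3 says AEs are "summarized for the Safety Analysis Set and de-registered subjects", which might suggest that the SAP pooled groups the protocol kept apart. But Protocol 21.1 and 6.1.6 both place de-registered subjects inside the safety set, so the SAP follows the protocol's definition. Nor did dropping the as-treated population remove a planned safety table, since the protocol assigned it none.
- d may be very small. De-registration applies only after angiographic eligibility and successful wire crossing. In the bare-metal predecessor studies, device, lesion and procedure success ran from 97.2% to 100% (Protocol 3.3.1 and 3.3.3), although those figures do not measure de-registration.
- Safety is descriptive, with no comparison with BIONICS, and SAP 10 reports the number in each population. A reader could rescale approximately.

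Rescaling works only for events known to be absent among de-registered patients, and the pooled tables do not show which those are. Keeping these patients for peri-procedural events and device deficiencies is right, and the point does not dispute it.

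**Conclusion.** The concern holds in a limited form. The AE, SAE, USADE and relatedness tables of SAP 17.1 default to a set that mixes stented patients with unstented patients whose follow-up is truncated, and no AE table is specified for exposed patients.

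If the set total is the denominator, percentages of device- or drug-related and late-onset events are understated by the factor 100/(100+d): about 1–2% relative at d = 1–2, 4.8% at d = 5 and 9.1% at d = 10. This assumes 100 FAS patients and no such events recorded among the de-registered. The number d is unknown, so these figures are a range and not an estimate.

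The direction for any-AE and procedure-related rates is uncertain. The FAS analyses of the adjudicated endpoints and of site-reported bleeding are not affected. De-registration is also not the only source of dilution, because patients who withdraw early stay in a crude denominator too.

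**What to change.** In SAP 17.1:

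- Make the main column of the AE, SAE, USADE and relatedness tables the patients with at least one MedJ-01 stent implanted. The already defined FAS is an acceptable alternative, but it retains patients in whom the stent was advanced and not implanted. If the FAS is used, the two rules in SAP 6.2 (de-registration for non-device reasons, and retention once the stent has passed the guiding catheter) should be reconciled for a patient who meets both.
- Show de-registered patients in a separate column, and keep the pooled Safety Set as a total for peri-procedural events and device deficiencies.
- State the denominator of the AE percentages in the SAP text, and show the number still in follow-up at each time point from 1 to 5 years. This also exposes the effect of early withdrawals.

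The cost is SAP wording and an extra table column. No new data are needed. Device-related and late AE percentages would become slightly less favourable.

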7. GENERAL CONSIDERATIONS

7.1. SUMMARY STATISTICS

Descriptive statistics of continuous variables will include number of observations available, mean, standard deviation, median, minimum, maximum, first quartile, and third quartile.

For categorical variables, the number within each category and the percentage out of the total number of observations available will be summarized. For that purpose, all variables with values missing, 'Unknown' or with values associated with 'Not applicable', 'Not Done', 'Not Reported' or 'Not Answered' will be set to missing and will not be included in the denominator for percentage calculation.

7.2. STUDY DAY

Study Day will be calculated from the date of enrollment (Day 1 is the day of enrollment), and will be used

Document: T:\PROJ\Medinol\CXA27472\06 Biostatistics\Documentation\SAP\Final

1.0_08Aug2018\JNIR01_SAP_Final V1.0_08Aug2018.docx

Author: [name] Version Number: Final V1.0 Version Date: 08Aug2018

Template No: CS TP BS016 Revision 4 Reference: CS WI BS005

Effective Date: 01Apr2016

Copyright © 2009, 2010, 2012, 2016 Quintiles Transnational Corp. All rights reserved.

to show start/stop day of assessments and events in the listings.

- If the date of the event is on or after the enrollment date then: Study Day = (date of event – enrollment date) + 1.
- If the date of the event is prior to the enrollment date then: Study Day = (date of event – enrollment date).

In the situation where the event date is partial or missing, Study Day, and any corresponding durations will appear missing in the listings.

7.3. RETESTS, UNSCHEDULED VISITS AND EARLY TERMINATION DATA

In general, for by-visit summaries, data recorded at the nominal visit will be presented. Unscheduled measurements will not be included in by-visit summaries, but will contribute to the best/worst case value where required (e.g. shift table).

Listings will include scheduled, unscheduled, retest and early discontinuation data.

7.4. WINDOWING CONVENTIONS

Follow up visits (windows) are scheduled at the following time points post procedure: 30 days (±7 days), 6 months (± 30 days), 1 year (-30 days/+14 days), and 2, 3, 4, and 5 years (± 60 days).

7.5. STATISTICAL TESTS

Only non-inferiority of JNIR01 Target Lesion Failure at 12 months (TLF₁₂) to the BIONICS TLF₁₂ will be formally tested in this trial. The secondary endpoints will not be formally tested for non-inferiority and testing will be considered descriptive. Details are given in Section 15.

7.6. SOFTWARE VERSION

All analyses will be conducted using SAS version 9.4 or higher.

Document: T:\PROJ\Medinol\CXA27472\06 Biostatistics\Documentation\SAP\Final

1.0_08Aug2018\JNIR01_SAP_Final V1.0_08Aug2018.docx

Author: [name] Version Number: Final V1.0 Version Date: 08Aug2018

Template No: CS TP BS016 Revision 4 Reference: CS WI BS005

Effective Date: 01Apr2016

Copyright © 2009, 2010, 2012, 2016 Quintiles Transnational Corp. All rights reserved.

8. STATISTICAL CONSIDERATIONS

8.1. ADJUSTMENTS FOR COVARIATES AND FACTORS TO BE INCLUDED IN ANALYSES

No adjustments for covariates are planned for the statistical analyses.

8.2. MULTICENTER STUDIES

Because a small number of patients are expected at each center, data from all centers will be pooled and no center effect will be investigated.

8.3. MISSING DATA

Missing data will not be imputed (except for the purpose of reporting adverse events and medications by time point, see APPENDIX 2 for partial date imputation conventions).

All available data will be included in the safety analysis. Some efficacy analyses are based on excluding patients who do not have adequate follow-up time.

8.4. MULTIPLE COMPARISONS/ MULTIPLICITY

Only non-inferiority of JNIR01 TLF₁₂ to the BIONICS TLF₁₂ will be formally tested in this trial and therefore no multiplicity adjustment will be performed. The secondary endpoints will not be formally tested for non-inferiority and testing will be considered descriptive.

8.5. ACTIVE-CONTROL STUDIES INTENDED TO SHOW NON-INFERIORITY OR EQUIVALENCE

JNIR01 is aimed at assessing TLF at one year with the MedJ-01 stent in a Japanese patient population to show non-inferiority of JNIR01 TLF₁₂ to the BIONICS TLF₁₂.

The non-inferiority margin will be set to 0.05 (5%). This margin, 1.5 times that of BIONICS, leverages a reasonable clinical threshold with safety concerns over sample size.

If the one-sided 90% confidence interval for the upper bound of the difference (JNIR01 TLF₁₂ minus BIONICS TLF₁₂) is less than this pre-specified non-inferiority margin, then the null hypothesis is rejected.

Details of the statistical method used to test non-inferiority are given in Section 15.1.

Document: T:\PROJ\Medinol\CXA27472\06 Biostatistics\Documentation\SAP\Final

1.0_08Aug2018\JNIR01_SAP_Final V1.0_08Aug2018.docx

Author: [name] Version Number: Final V1.0 Version Date: 08Aug2018

Template No: CS TP BS016 Revision 4 Reference: CS WI BS005

Effective Date: 01Apr2016

Copyright © 2009, 2010, 2012, 2016 Quintiles Transnational Corp. All rights reserved.

8.6. EXAMINATION OF SUBGROUPS

No subgroup analyses will be performed for this study.

9. OUTPUT PRESENTATIONS

APPENDIX 1 shows conventions for presentation of data in outputs.

The templates provided with this SAP (separate document) describe the presentations for this study and therefore the format and content of the summary tables and listings to be provided by IQVIA Biostatistics and Cardiovascular Research Foundation.

